2.3.2.1 Risks Associated with Radiation Exposure

¹²⁴I is one of several radioactive isotopes of iodine commonly used in human research and medical care with a radioactive half-life of 4.2 days. The clinically important risk of exposure to ¹²⁴I derives from the potential sequestration of iodine in the thyroid gland and the concentration of radiation exposure in that gland. Subjects exposed to ¹²⁴I as ¹²⁴I-AT-01 will be treated with three daily doses of nonradioactive elemental iodine (¹²⁷I), administered as potassium iodide (KI), at recommended doses beginning >30 minutes and within 24 hours prior to dosing. No other clinically important untoward effects of this well-characterized iodine isotope are expected at the doses planned in this study.

From Study AMY1001, the gender-averaged mean whole-body effective radiation dose associated with 124 I-AT-01 was 0.24 ± 0.02 mSv/MBq. Therefore, the 1 mCi dose used for each dose in this study will result in an estimated whole-body effective dose of \sim 8.7 mSv associated with the radiotracer. The whole blood radioactivity half-life was 21.9 hours. Whole blood

radioactivity levels were <100 Bq/mL at 48 hrs following a single 1 mCi dose of ¹²⁴I-AT-01 (Wall 2021).

Subjects will also be exposed to radiation from the PET/CT imaging. To reduce radiation dose from the PET/CT protocol, image acquisition will use a low-dose CT for attenuation correction.

Women of childbearing potential must also agree to remain as abstinent (refrain from heterosexual intercourse) or use contraceptive methods that result in a failure rate of <1% per year during the treatment period and for at least 90 days after the last dose of study intervention. Men with female partners of childbearing potential must also agree to remain abstinent or use a condom plus an additional contraceptive method that together result in a failure rate of <1% per year during the treatment period and for at least 30 days plus 90 days (a spermatogenesis cycle) after the last dose of study intervention. Men must also agree to refrain from donating sperm during this same time period. Additional details are provided in Section 5.1.

2.3.2.2 Risks Associated with Exposure to the Virus SARS-CoV-2

In consideration of the Coronavirus disease (COVID-19) pandemic caused by the virus SARSCoV-2 and the impact it may have on clinical trials, COVID-19 related risks to subjects are carefully considered and will be documented on an ongoing basis. Measures that prioritize trial subject safety and data integrity have been developed in consideration of local guidelines. To minimize risk of exposure associated with trial participation, the Schedule of Activities (SoA) (Section 1.3) has been optimized to allow for an adequate follow-up and assessment of the safety of ¹²⁴I-AT-01, without unnecessarily increasing subject exposure.

As the pandemic situation evolves, the Sponsor will reassess risks, which will be documented as part of the Sponsor's trial master file. If escalation of the pandemic during this trial and local circumstances lead to a local change in risk assessment, additional measures may be implemented. In this case, an Investigator-driven risk assessment will be conducted and documented in the Investigator's site master file and communicated to the Sponsor.

2.3.3 Benefit/Risk Conclusion

The potential benefits of having a comprehensive assessment of the extent of amyloid deposits in subjects with systemic amyloidosis have been considered against the risks associated with (i) ¹²⁴I-AT-01, (ii) the study procedures, (iii) the method of administration, and (iv) the COVID-19 pandemic. Subjects in this study will be closely monitored for potential risks. Eligibility criteria excludes subjects with higher risk, including those with significant co-morbidity such as Eastern Cooperative Oncology Group (ECOG) score of 3 or greater, New York Heart Association (NYHA) Class IV heart failure, or other ongoing serious illness.

For patients with systemic amyloidosis, there is a substantial medical need for amyloid-specific imaging diagnostics. Therefore, the Sponsor considers that the value of the information to be gained outweighs the risks associated with participating in this study.

3.0 OBJECTIVES AND ENDPOINTS

| Objective | Endpoint | | |
|---|--|--|--|
| Primary | | | |
| To evaluate the repeatability of organ-specific quantitation of radiotracer uptake following PET/CT imaging of ¹²⁴ I-AT-01 in subjects with AL or ATTR systemic amyloidosis. | Repeatability coefficient (Bland-Altman plots) and ICC associated with the quantification of radioactivity associated with organ level 124I-AT-01 uptake measurements. | | |
| Secondary | | | |
| To characterize the safety and tolerability of repeat doses of ¹²⁴ I-AT-01 administered by IV infusion or slow IV bolus. | Incidence of treatment-emergent AEs¹ from Day 1 to EOS. | | |
| | Change from Baseline in clinical laboratory values ² at Visits 2 and Safety Follow-up 1 (1-3 days after the second administration of ¹²⁴ I-AT-01). | | |
| | Change from Baseline in vital signs. | | |
| | Change from Baseline in ADA. | | |

Abbreviations: ADA = anti-drug antibodies; AEs = adverse events; AL = amyloid light chain; ATTR = amyloid transthyretin; CT = computerized tomography; EOS = end of study; ICC = intraclass correlation coefficient; IV = intravenous; PET = positron emission tomography.

- 1. Adverse events will be graded using National Cancer Institute Common Terminology Criteria for Adverse Events (CTCAE) version 5.
- 2. Clinical laboratory tests are described in Section 10.2 and include hematology and serum chemistry.

- 21 -

4.0 STUDY DESIGN

4.1 Overall Design

This is a multicenter, open-label, single arm study in subjects with AL or ATTR systemic amyloidosis. ¹²⁴I-AT-01 is the only study intervention; neither reference therapy nor placebo will be administered.

This study consists of a screening period of up to 30 days; two, one-day treatment periods (Day 1 and Week 6); a safety follow-up 1-3 days after the second administration of 124 I-AT-01, and a final safety follow-up 28 ± 3 days after the second administration of 124 I-AT-01. Thus, the total subject duration is approximately 14 weeks.

Adverse events will be monitored and recorded from Screening through the final safety follow-up/EOS. The schedule for all screening, treatment, and follow-up period activities is provided in the SoA (Section 1.3).

4.1.1 Screening Period

The screening period is up to 30 days. Eligibility criteria (Section 5.0) will be confirmed and informed consent, as specified in Section 10.1.3, will be obtained. Blood and urine tests as outlined in the SoA (Section 1.3) will be obtained during the screening period.

In WOCBP, serum pregnancy and all other laboratory samples must be drawn within 7 days prior to ¹²⁴I-AT-01 administration. The results of the pregnancy test must be available and be negative prior to ¹²⁴I-AT-01 administration in all WOCBP.

4.1.2 Pre-Administration Period

Subjects will begin therapy with KI 130 mg (e.g., iOSAT, Potassium Iodide Oral Solution USP, 65 mg/mL) orally once every day for 3 days beginning at least 30 minutes and within 24 hours prior to dosing with ¹²⁴I-AT-01 on the Day 1 and Week 6 visits to block radioactive iodine uptake in the thyroid gland.

4.1.3 Administration Period

Administration of ¹²⁴I-AT-01 and the associated study procedures occur at the Day 1 and Week 6 (+ 2 week) visits. Administration of ¹²⁴I-AT-01 and the associated study procedures are described in Section 4.1.3.1.

4.1.3.1 Administration of Study Intervention(s) and Associated Procedures Day 1 and Week 6 (+ 2 week) Visits

The schedule for administration of ¹²⁴I-AT-01 is provided in the SoA (Section 1.3). Administration of ¹²⁴I-AT-01 occurs at the Day 1 and Week 6 to Week 8 visits, as follows:

Prior to Administration of ¹²⁴I-AT-01

- 1) Clinical laboratory tests and biomarker analysis (including serum pregnancy test in WOCBP) will be obtained within 7 days prior to the second administration of ¹²⁴I-AT-01, as described in the SoA (Section 1.3). The results of the pregnancy test must be available and be negative prior to ¹²⁴I-AT-01 administration in all WOCBP.
- 2) Instruct subject to take oral KI daily for 3 days, as described in Section 4.1.2.
- 3) Record concomitant medications and monitor and record AEs throughout the study visit.

Administration of ¹²⁴I-AT-01

4) Subjects enrolled under protocol Version 2.0 will receive a single dose of 1 mCi (± 10%) 124I-AT-01 by slow IV bolus at a rate of 1 mL/ 5 seconds. During 124I-AT-01 administration, monitor subjects for infusion-related reactions (IRRs), as described in Section 7.1.1. For all subjects, 124I-AT-01 will be administered by the same route (IV infusion over 2-5 minutes or slow IV bolus at 1 mL/5 seconds) at the Week 6 visit as on the Day 1 visit.

After Completion of Administration of ¹²⁴I-AT-01

- 5) Blood pressure and heart rate will be measured 5-10 minutes after administration of ¹²⁴I-AT-01.
- 6) Subjects will undergo a PET/CT scan 5 hours (± 30 minutes) after the start of administration of ¹²⁴I-AT-01 to quantify ¹²⁴I-AT-01 uptake in organs. ¹²⁴I-AT-01 whole-body scans will be acquired by study-designated PET/CT scanners, as described in Section 8.1.4.
 - Subjects will be discontinued if amyloid deposits are not identified in the Day 1 PET/CT scan in at least one of the following organs: heart, liver, spleen or kidney (i.e., they will not receive a second administration of ¹²⁴I-AT-01 or undergo a second scan) and will undergo early termination (ET) activities, as provided in the SoA (Section 1.3) and as described in Section 4.1.5.
- 7) Any adverse events will be recorded; patient can be discharged after completing the scan and deemed stable by study staff.

4.1.4 Follow-up Period

As shown in the SoA (Section 1.3), the follow-up period is 28 +/- 3 days after the second administration of ¹²⁴I-AT-01. It consists of the following:

- Safety Follow-up 1: a safety follow-up phone call 1-3 days after the second administration of ¹²⁴I-AT-01 and a safety laboratory draw 1-3 days after the second administration of ¹²⁴I-AT-01; and
- Safety Follow-up 2: a final safety follow-up phone call 28 ± 3 days after the second administration of ^{124}IAT -01 for collection of AEs and concomitant medication, and a blood draw 28 ± 3 days after the second administration of ^{124}I -AT-01 for anti-drug antibodies (ADA).

Blood draws for laboratory and ADA will be collected locally by visiting nurse/phlebotomist.

Both Safety Follow-up 1 and Safety Follow-up 2 activities will be conducted for subjects who discontinue for IRRs, as described in Section 7.1.1.1, at either the first or second administration of ¹²⁴I-AT-01.

4.1.5 Early Termination Visit

Subjects that are withdrawn or discontinued per the criteria provided in Section 7.1 will undergo the ET activities provided in the SoA (Section 1.3) within 7 days from the early termination decision. Blood draw for ADA should be obtained if ET is ≥4 weeks after the first administration of ¹²⁴I-AT-01 of ¹²⁴I-AT-01 and will be collected locally by visiting nurse/phlebotomist.

ET activities do not apply to subjects discontinued for IRRs. Safety Follow-up 1 and Safety Follow-up 2 activities (Section 4.1.4) will be conducted for subjects who discontinue for IRRs at either the first or second administration of ¹²⁴I-AT-01.

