1.3 Schedule of Activities

| Visit | Screening | Vis Da | it 1/ y 1 | | it 2/ ek 6 | Safety Follow-up 1 ^j | Safety Follow-up 2 (EOS) ^j | Early Termination (ET) k,l |
|--|------------------------|---------------------------------|------------------------------------|---------------------------------|------------------------------------|------------------------------------|---|--------------------------------|
| Window | Day -30 to Day 1 | ± 0 | days | Week 6 t | o Week 8 | 1-3 Days After Visit 2 | 28 (± 3) Days After Visit 2 | <7 days from ET Decision |
| Timing of Activity(ies) | | Prior to ¹²⁴ I-AT-01 | ¹²⁴ I-AT-01 and Scan | Prior to ¹²⁴ I-AT-01 | ¹²⁴ I-AT-01 and Scan | | | |
| Assessment/Procedures | | | | | | | | |
| Informed Consent a | X | | | | | | | |
| Medical history and Demographics | X | | | | | | | |
| Inclusion and Exclusion criteria | X | | | | | | | |
| Concomitant Medications | X | X | X | X | X | X | X | X |
| Oral Potassium Iodide (KI) ^b | | X | | X | | | | |
| ¹²⁴ I-AT-01 Administration ^c | | | X | | X | | | |
| Biomarker and Safety Assessments | | | | | | | | |
| Vital Signs (HR and BP) d | | X | X | X | X | | | |
| Body Weight | | X | | X | | | | |
| Height | | X | | | | | | |
| Pregnancy Test (WOCBP) e,f | X | | | X | | | | |
| PET/CT Scan | | | X | | X | | | |
| Adverse events g | X | X | X | X | X | X | X | X |
| Laboratory h,i | X | | | X | | X | | |
| Biomarkers h,i | X | | | X | | | | |
| Urine UACR (AL subjects only) i | X | | | X | | | | |
| Serum ADA i | X | | | X | | | X | X |

Abbreviations: ADA = anti-drug antibodies; AL = amyloid light chain amyloidosis; BP = blood pressure; CBC = complete blood count; EOS = end of study; ET = early termination; HR = heart rate; NT-proBNP = N-terminal prohormone of brain natriuretic peptide; UACR = urine albumin-to-creatinine ratio; WOCBP = women of childbearing potential.

- a. Informed consent, as described in Section 10.1.3.
- b. KI is self-administered by the subject daily for 3 days, beginning >30 minutes and <24 hr prior to dosing, as described in Section 4.1.2.
- c. ¹²⁴I-AT-01 will be administered by IV infusion over 2-5 minutes (protocol Version 1.1) or slow IV bolus at 1 mL/5 seconds (protocol Version 2.0), as described in Section 4.1.3. For all subjects, ¹²⁴I-AT-01 will be administered by the same route (IV infusion over 2-5 minutes or slow IV bolus at 1 mL/5 seconds) at the Week 6 visit as on the Day 1 visit.

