- d. Subjects must remain semi-recumbent for at least 5 minutes prior to blood pressure measurements. Blood pressure and heart rate will be measured within an hour prior to dosing and 5-10 minutes after administration of ¹²⁴I-AT-01.
- e. Serum pregnancy test, as indicated in Section 10.2, will be obtained in all women of childbearing potential.
- f. Serum pregnancy and all other laboratory samples must be drawn within 7 days prior to administration of ¹²⁴I-AT-01 in all WOCBP. The results of the pregnancy test must be available and be negative prior to ¹²⁴I-AT-01 administration in all WOCBP.
- g. Adverse events will be monitored from Screening through the EOS Visit. For Safety Follow-up 1 and 2, adverse events and concomitant medications can be obtained by phone call.
- h. Clinical laboratory tests and biomarker analysis, as described in Section 10.2. Baseline sample will be collected within 30 days prior to the first administration of ¹²⁴I-AT-01; second sample within 7 days prior to the second administration of ¹²⁴I-AT-01; third sample at Safety Follow-up 1 after the second administration of ¹²⁴I-AT-01.
- i. Urine and blood may be collected locally by visiting nurse/phlebotomist. An additional serum ADA sample will be obtained at Screening for subjects who provided consent for the extra ADA sample.
- j. Safety follow-ups for concomitant medications and adverse events will be done via telephone call for all subjects. Both Safety Follow-up 1 and Safety Follow-up 2 activities will be conducted for subjects who discontinue for IRRs at either the first or second administration of ¹²⁴I-AT-01.
- k. Blood draw for ADA should be obtained if ET is ≥4 weeks after first administration of ¹²⁴I-AT-01.
- l. Early Termination activities do not apply to subjects discontinued for IRRs. Please follow Safety Follow-up 1 and Safety Follow-up 2 activities for subjects experiencing IRR with either the first or second administration of ¹²⁴I-AT-01.

- 15 -

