7.0 DISCONTINUATION OF STUDY INTERVENTION AND/OR SUBJECT DISCONTINUATION OR WITHDRAWAL

7.1 Discontinuation of Study Intervention

All subjects are free to withdraw from participating in this study at any time for any reason, specified or unspecified, and without prejudice. No constraints will be placed on ordinary subject management.

Subjects will be withdrawn for any of the following reasons:

- The subject withdraws consent.
- The subject does not have amyloid deposits in the heart, liver, spleen or kidney on the Day 1 PET/CT scan, as described in Section 8.1.4.
- The subject begins treatment with heparin or a heparin analog within 7 days of a planned administration of ¹²⁴I-AT-01, as described in Section 7.1.1.2.
- The subject experiences an intolerable AE or serious AE (SAE).
- The subject enrolls into another clinical study in which an investigational treatment or approved therapy for investigational use is administered.
- The subject becomes pregnant. Study treatment must be discontinued immediately. Report the pregnancy according to the instructions in Section 8.3.5.
- The subject is unwilling or unable to comply with the protocol.
- At the discretion of the Investigator or Sponsor.
- Investigator decision that it is not in the best medical interest of the subject to continue participation in the investigation.
- The Sponsor prematurely terminates the study.

Prior to discontinuing a subject, every effort should be made to obtain as much follow-up data as possible. Withdrawn or discontinued subjects will undergo ET activities per the SoA (Section 1.3). Subject withdrawals will be documented clearly on the source documents and applicable case report forms (CRFs). Subject withdrawals will be documented clearly on the source documents and applicable CRFs.

Discontinued subjects will be assessed for adverse events via a telephone call 24-48 hours after decision to discontinue.

Notification of subject withdrawals will be made to the Sponsor, or designee.

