7.1.1 Specific Stopping Criteria

7.1.1.1 Infusion-related Reactions

Infusion-related reactions (IRRs) can be any signs or symptoms experienced by subjects during the infusion of pharmacologic or biologic agents or any event occurring on the first day of the infusion (Doessegger 2015). IRRs have been reported, among other terms, as anaphylaxis, anaphylactoid reactions, cytokine release syndrome, hypersensitivity reaction, etc. Symptoms suggestive of an IRR include but not limited to the following: tachypnea with respiratory distress, new onset rash or pruritus, chills, stridor, wheezing, swollen or itchy lips or tongue, onset of abdominal cramping, or hypotension.

Treatment-emergent adverse events starting on the day of ¹²⁴I-AT-01 administration will be summarized to evaluate potential infusion-related reactions.

Subjects will be monitored for IRRs and managed as follows:

- During administration of ¹²⁴I-AT-01: if an IRR occurs during administration, the administration will be immediately discontinued and the subject will be treated for their symptoms and discontinued from the study. Activities for Safety Follow-up 1 (1-3 days after the second administration) and Safety Follow-up 2/EOS (28 (± 3) days after the second administration) will be conducted, per the SoA (Section 1.3).
- After administration of ¹²⁴I-AT-01: if an IRR occurs in a subject after completion of the administration, the subject will be treated for their symptoms, managed in accordance with standard of care, and the IRR will be recorded as an AE. If the symptoms respond promptly to minimal intervention (e.g., responds promptly to symptomatic treatment with antihistamines, acetaminophen, or nonsteroidal anti-inflammatory drugs (NSAIDs)) then, at the discretion of the Investigator, the subject may continue in the study. If the symptoms are prolonged (e.g., not rapidly responsive to symptomatic medication), require IV fluids or treatments, or require hospitalization, the subject will be discontinued from the study. Activities for Safety Follow-up 1 (1-3 days after the second administration) and Safety Follow-up 2/EOS (28 (± 3) days after the second administration) will be conducted, per the SoA (Section 1.3).

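### Subjects stopped early after one dose for a reason other than an infusion-related reaction can leave safety observation about 8 days after dosing, with no post-dose anti-drug antibody sample scheduled

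*Protocol*

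**What the plan says.** Protocol 4.1.3.1 has a built-in stopping rule: "Subjects will be discontinued if amyloid deposits are not identified in the Day 1 PET/CT scan" in heart, liver, spleen or kidney. Such a subject gets no second dose or scan and goes to ET activities.

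ET is timed from the decision. Section 4.1.5 says these subjects "will undergo the ET activities provided in the SoA (Section 1.3) within 7 days from the early termination decision"; the ET column of the Schedule of Activities (SoA) has "<7 days from ET Decision". Section 7.1 adds one contact inside that window: "Discontinued subjects will be assessed for adverse events via a telephone call 24-48 hours after decision to discontinue".

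The ADA sample at ET is conditional. SoA note k: "Blood draw for ADA should be obtained if ET is ≥4 weeks after first administration of" the tracer. The other post-dose ADA samples are at Visit 2 and Safety Follow-up 2, which this subject does not reach.

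Safety Follow-up 2, the AE call with an ADA draw, belongs to a period dated from the second dose. Section 4.1.4: "the follow-up period is 28 +/- 3 days after the second administration of" the tracer. It is extended to one-dose subjects only when they stop for an infusion-related reaction (IRR). SoA note j: "Both Safety Follow-up 1 and Safety Follow-up 2 activities will be conducted for subjects who discontinue for IRRs", whether the reaction was at the first or the second dose. Section 7.1.1.1 nevertheless dates those contacts from a second dose: "Safety Follow-up 2/EOS (28 (± 3) days after the second administration) will be conducted".

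**The concern.** Two subjects who each received one dose are followed differently according to why they stopped. The one with an IRR is meant to have a 28-day call and an ADA draw. The one with a negative scan, or any other early non-IRR stop, may have neither, and the protocol gives no reason for the difference.

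Section 4.2.3 defends 28 days of follow-up after the second dose as more than five half-lives. Section 8.3.1 records AEs up to the end-of-study call, but no such call is scheduled for this group. The SAP does not close the gap: section 9 places ADA outside its scope, and Table 8-1 dates the combined end-of-study and ET window from the second infusion.

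These subjects received drug, so they are in the Safety Set (SAP 5) and count fully in the denominator of AE percentages (SAP 9.3.1). Change in ADA is a secondary endpoint, and immunogenicity is a named risk in Protocol Table 1. A later AE, or an antibody response to the single dose, has no scheduled contact at which to be recorded.

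**Working it through.** Day 0 is the day of dose 1.

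**Inputs.** Physical half-life 4.2 days (Protocol 4.2.3, 6.2). Whole-blood half-life 21.9 hours (2.3.2.1). ET up to 7 days after the decision (4.1.5). ADA at ET from 28 days after dose 1. Up to 20 subjects (9.3). The time from scan to decision is not stated, so it is varied.

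**The plan's own figures.** 28 / 4.2 = 6.7 half-lives, which is more than five. 10 × 4.2 = 42 days, or 6 weeks. Both statements in 4.2.3 reproduce.

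**Last scheduled contact** = decision day + 7.

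| Decision day (assumed) | Last contact by day | Half-lives (day / 4.2) | ADA possible at ET |
|---|---|---|---|
| 0 | 7 | 1.7 | no |
| 1 | 8 | 1.9 | no |
| 7 | 14 | 3.3 | no |
| 14 | 21 | 5.0 | no |
| 20 | 27 | 6.4 | no |
| 21 | 28 | 6.7 | yes |

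The SoA's stricter wording shortens each contact by a day: a day-1 decision then ends by day 7 (1.7 half-lives).

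**ADA cut-off.** Decision + 7 < 28 gives decision < day 21. On the SoA wording, decision + 6 < 28 gives < day 22. A decision before day 21 therefore yields no ADA sample on either reading. A heparin stop near Week 6 falls at day 42 − 7 = 35 or later, so ADA is already due at ET.

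**Blood activity.** 8 × 24 / 21.9 = 8.8 whole-blood half-lives by day 8. The gap therefore concerns AE and ADA observation, not circulating activity.

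**Observation after one dose, compared.** A continuing subject's AEs after dose 1 are collected up to Visit 2 at Week 6 to 8: 8/42 = 19%, 8/56 = 14%. Against the 28 days meant for a one-dose IRR stop: 8/28 = 29%.

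**Number affected.** The earlier study found uptake in one or more organs in more than 90% of patients, mostly at 2 mCi (2.2.2, 4.3). Here the dose is 1 mCi, only four organs count, and clinical organ involvement is required, so the negative rate could be higher or lower. Assumed rates, which are not bounds:

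| Negative rate p | Expected, 20p | At least one, 1 − (1 − p)^20 |
|---|---|---|
| 2% | 0.4 | 33% |
| 5% | 1.0 | 64% |
| 10% | 2.0 | 88% |

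**Effect on AE incidence.** Section 5.5 replaces such subjects, so one of them is 1 of 21 in the Safety Set. If that subject's first treatment-emergent AE falls after the last contact and is missed, incidence is understated by 1/21 = 4.8 points. With a constant event rate and an assumed 28-day risk p, the chance of a first event between days 8 and 28 is (1 − p)^(8/28) − (1 − p):

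- p = 20%: 0.138; divided by 21, 0.7 points expected.
- p = 40%: 0.264; divided by 21, 1.3 points expected.

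**The case against.** The strongest reply is that the split is deliberate. The protocol separates IRR from non-IRR stops in several places, and subjects who reacted to the drug have the clearer need for follow-up. The secondary objective concerns repeat doses, continuing subjects already give an ADA sample after one dose (before dose 2), and the earlier study covered single doses in 57 subjects, mostly at twice this activity. The 28-day rationale is written for the second dose and needs only about 21 days to pass five half-lives. Early stops are contacted sooner after dose 1 than continuing subjects, who have no scheduled contact before Visit 2. Patients are told to report symptoms (Table 1, 8.3), unscheduled visits are allowed (8.2.4), related SAEs are followed (8.3.3), sites are urged to gather follow-up data before discontinuing a subject (7.1), and they may report related SAEs after discontinuation (8.3.2).

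Much of this stands as mitigation. None of it schedules a later contact or an ADA draw. Continuing subjects are asked about AEs at Visit 2, so their interval after dose 1 is covered, although late. The ≥4-week condition shows that the protocol does not call for an earlier ADA sample at ET, yet nothing later is scheduled for these subjects. The reply is right that day 8 depends on an assumed decision day, that the AE figures are illustrative, and that a 28-day call would not equalise exposure with two-dose subjects. It is also right that the second-dose anchor in 7.1.1.1 is, taken alone, an editorial fault, since the intent is clear from 4.1.4, 4.1.5 and SoA notes j and l.

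**Conclusion.** The concern holds. A one-dose, non-IRR stop decided before day 21 has no scheduled post-dose ADA sample and no assured contact at 28 days, while a one-dose IRR stop is meant to have both. With a day-1 decision, contact ends by day 8; a slower read lengthens it, and a day-14 decision reaches day 21. The number is probably small: 0.4 to 2 of 20 on the assumed 2-10% of negative scans, plus any other early non-IRR stops. With one such subject, the expected understatement of AE incidence is 0.7 to 1.3 points under the assumed risks, and 4.8 points at worst. The study is descriptive, and these subjects are outside the Image Evaluable Set, so the primary result is not affected. This is a worthwhile, inexpensive improvement in safety observation.

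**What to change.** In 4.1.5 and SoA notes k and l:

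- Keep the ET contact, and keep the rule that ADA is drawn at ET from 4 weeks after dose 1, so late stops lose nothing.
- Add that any dosed subject who has not withdrawn consent, and whose ET contact falls before day 25 after the last dose received, has the Safety Follow-up 2 AE/SAE call and ADA draw at 28 ± 3 days after that dose.
- Let an ET contact on days 25-27 count as Safety Follow-up 2, with ADA drawn then. Those days are inside the 25-31 day window but fall short of the 4-week condition.

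In 7.1.1.1 and 4.1.4, date IRR follow-up from the last dose received. Matching wording in SAP Table 8-1 would be for consistency only.

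The cost is a few sentences, one telephone call and one visiting-nurse draw per affected subject, and no additional safety laboratory panel. As a protocol amendment it needs ethics committee approval before use (10.1.1), and the consent form may need a matching change.
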